### **8.4      Pharmacokinetic Evaluations**

Samples for PK analysis will be collected as indicated per the SOE.

Blood samples will be obtained from all subjects to assess PK parameters of QR-110 ( $AUC_{0-\infty}$ ,  $AUC_{0-t_{last}}$ ,  $C_{max}$ ,  $C_0$ ,  $T_{max}$ ,  $T_{1/2}$ ,  $CL$ ,  $V_d$ ) pre- and post-dosing as indicated per the SOE (Appendix 1).  $T_{1/2}$  and  $V_d$  will only be evaluated if measurable serum levels are obtained.

## 8.5 Electrocardiogram

Twelve-lead ECG will be obtained as indicated per the SOE. Electrocardiograms should be done in triplicate after the subject has been resting comfortably in a supine position for a minimum of 8 minutes. The mean of triplicate results will be captured in the eCRF.

A repeat of ECGs (in triplicate) is permitted to confirm potentially spurious results, at the discretion of the Investigator. Repeat analysis results should be discussed with the Sponsor Medical Monitor. Details on the conduct of ECGs is provided in the Study Reference Manual.

## 8.6 Physical Examination

Complete and symptom-directed physical examinations (urogenital exams not required) will be performed as indicated per the SOE

## 8.7 Height and Weight

Height will be measured using a calibrated, wall-mounted stadiometer and will be documented as indicated per the SOE. Body weight will be measured using a calibrated scale as indicated per the SOE

## 8.8 Ophthalmic Exams

Ophthalmic examinations will be performed at all study visits. BCVA will also be assessed at specified time points as indicated per the SOE. The ophthalmic exam is comprised of: BCVA; anterior segment examination, including grading of anterior chamber inflammation according to the Standardization of Uveitis Nomenclature (SUN) Working Group Grading Scheme for Anterior Chamber Flare; IOP; clinical lens grading using the Age-Related Eye Diseases Study (AREDS) Clinical Lens Grading System (ARLNS); posterior segment/fundus examination including grading inflammation in the vitreous using the National Institute of Health (NIH) Grading Scale for Vitreous Haze.

The procedures for ophthalmic exams are outlined in the Study Reference Manual.

## 8.9 Optical Coherence Tomography

Changes in OCT findings are of relevance to the safety profile of QR-110. Optical Coherence Tomography images will be evaluated for changes in the remaining volume of ONL and foveal thickness as safety parameters. All OCT scans should be performed in accordance with the procedures outlined in the Image Acquisition and Submission Protocol.

The DMC and Sponsor Medical Monitor should review all OCT scans, with particular attention to identifying changes including, remaining volume of ONL, foveal thickness, appearance of cystoid macular edema, or macular edema as compared to baseline.

### **8.10 Leber's Congenital Amaurosis Genetic Analysis**

Genotyping results (either historic or at screening) are required for eligibility. For subjects without an acceptable historic genotyping result, genotyping and sequencing of genes associated with inherited retinal dystrophies will be performed at Screening. Separate informed consent may need to be obtained per local requirements. A blood sample for genotyping and gene sequencing should be obtained at the Screening Visit.

### **8.11 Biomarkers**

and stored for later quantification. In addition, blood samples for biomarkers may be collected at any study visit at which inflammation, pain or redness of the eye is present, including any unscheduled visits.

### **8.12 Efficacy Assessments**

Subjects must perform all Screening examinations. If a subject is unable to perform a specific assessment at a subsequent visit, this should be recorded in the eCRF and the subject's ability reassessed at the next specified visit. All attempts at performing assessments should be recorded in the eCRF.

Most measures of visual function (BCVA, FST, mobility course, oculomotor instability, PLR) will be measured a minimum of 2 times prior to the subject's first dose of study drug to evaluate intrasubject variability (Screening and predose on Day 1). Measures of retinal anatomy (infrared imaging and OCT) and ERG will be measured a minimum of 1 time prior to the subject's first dose of study drug. Any predose assessment may be repeated if the results are considered unreliable or of unacceptable quality by the Investigator or if the assessment could not be completed. In the case of repeat assessments, the measure reflecting the average of the measures will be considered the Baseline value.

If possible, photoreceptor outer segment layer thickness will be calculated from OCT images as an exploratory efficacy parameter. This assessment will be conducted for those subjects for whom high quality imaging to evaluate this parameter can be obtained, as determined by the investigator.

Narratives will be written for all participating subjects on an ongoing basis.

Exploratory efficacy response criteria will be obtained as indicated per the SOE

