PLR	Pupillary Light Reflex
PP	Per Protocol
PT	Preferred Term
RTF	Rich Text Format
SAE	Serious Adverse Event
SAP	Statistical Analysis Plan
SD	Standard Deviation
SDC	Statistics and Data Corporation, Incorporated
SOC	System Organ Class
$T_{1/2}$	Half-Life
TEAE	Treatment-Emergent Adverse Event
VA	Visual Acuity
V_d	Apparent Volume of Distribution
VEP	Visual Evoked Potential
VFQ-25	25-Item Visual Functioning Questionnaire
WHO DDE	World Health Organization Drug Dictionary Enhanced
WOCBP	Women of Childbearing Potential

1. Introduction

The purpose of this statistical analysis plan (SAP) is to describe the planned analyses and reporting in support of protocol PQ-110-001, version 6.0 dated 02-Aug-2018.

This SAP is being written with due consideration of the recommendations outlined in the most recent International Council for Harmonisation (ICH) E9 Guideline entitled Guidance for Industry: Statistical Principles for Clinical Trials and the most recent ICH E3 Guideline, entitled Guidance for Industry: Structure and Content of Clinical Study Reports.

This SAP describes the data that will be analyzed and the subject characteristics, efficacy, and safety assessments that will be evaluated. This SAP provides details of the specific descriptive statistical methods that will be used.

In addition to this SAP, inferential analyses will be generated by [REDACTED] which will also be used to support the CSR. The descriptions of methods and statistical analyses used for these inferential analyses are described separately within the scope of the Cytel SAP of which a copy has been included in whole in [REDACTED] and which should be read in conjunction with this SAP.

The statistical analysis methods presented in this document will supersede the statistical analysis methods described in the clinical protocol. If additional analyses are required to supplement the planned analyses described in this SAP they may be completed and will be identified in the Clinical Study Report (CSR). Study Objectives

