7.2.1 MISSING MOBILITY COURSE COMPOSITE SCORE IMPUTATIONS FOR CENTRAL READING CENTER GRADING

7.3 Definition of Baseline

Baseline is defined as the last measurement prior to the first dose of study drug in the treated eye for IOP, laboratory parameters, and the safety endpoints slit lamp biomicroscopy, posterior segment/fundus exam, vital signs, and ECG . For ophthalmic parameters BCVA, FST, mobility course, OCI and PLR measured at Screening and Visit 2 (Day 1) the average will be defined as baseline. For other ophthalmic parameters, NIRAF, SD-OCT, and ERG, planned to be done once at baseline, the average will be defined as baseline if the exam is repeated. Change from baseline will be calculated as follow-up visit/time point minus baseline visit/time point.

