14.3 Pupillary Light Reflex (PLR)

Pupillary Light Reflex (PLR) imaging will measure the pupil size in various candela per square meter stimulus (ie, at 4, 40, 400 and 4000 cd/m^2). Maximum amplitude, delayed amplitude at 0.9 sec and overall latency (time to react) will be measured according to the imaging schedule of Section 3.5 of the SAP and Imaging Charter.

The PLR values and changes from baseline for each eye (treated eye and contralateral eye) will be summarized using continuous descriptive statistics and 95% CIs by visit and eye for each dose group and for all subjects. Baseline PLR is the average of all pre-dose PLR assessments. A subject listing of PLR will also be produced.

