14.4 Oculomotor Instability (OCI)

Oculomotor Instability (OCI) will be measured with fixation and without fixation according to the imaging schedule of Section 3.5 of the SAP and Imaging Charter. The OCI values and changes from baseline for each eye (treated eye and contralateral eye) will be summarized using continuous descriptive statistics and 95% CIs by visit and eye for each dose group for all subjects. Baseline OCI is the average of all pre-dose OCI assessments. A subject listing of OCI will also be produced.

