14.5 Electroretinogram (ERG) in Scotopic and Photopic Conditions

Electroretinogram (ERG) will measure a-wave (initial corneal-negative deflection) and b-wave (corneal-positive deflection) under scotopic (low light conditions or dark adaptive measures) and photopic (normal light conditions or light adaptive measures) conditions. Dark adaptive oscillatory potentials, light adaptive flicker response, overall rod and cone waves and overall rod and cone functioning will also be assessed. ERG measurements will be taken in accordance to the imaging schedule of Section 3.5 of the SAP and the Imaging Charter.

The ERG values and changes from baseline for each eye (treated eye and contralateral eye) will be summarized using continuous descriptive statistics and 95% CIs by light/dark adaptive condition, visit and eye for each dose group for all subjects. Baseline ERG is the average of all pre-dose ERG assessments for that light/dark adaptive condition. A subject listing of ERG will also be produced.

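### The Screening acuity that picks the treated eye is also half of its BCVA baseline, which tilts the change toward benefit; separately, pre-dose readings rejected for quality stay in averaged baselines

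*Protocol*

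**What the plan says.** **Choice of eye and BCVA baseline.** The Protocol synopsis (Study Design) and SAP 2.1 and 7.1 assign the drug to the eye with worse visual acuity at Screening. If the acuities tie, FST or the mobility course score decides, and then the Investigator. For the ophthalmic parameters measured twice before dosing, SAP 7.3 says: "BCVA, FST, mobility course, OCI and PLR measured at Screening and Visit 2 (Day 1) the average will be defined as baseline". SAP 14.1 tabulates the BCVA change from this baseline by visit, for each eye. Protocol 2.3.1 puts most weight on two contrasts: treated eye against contralateral eye, and treated eye against its own baseline.

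**Repeated pre-dose tests.** Protocol 8.12 and the synopsis say: "Any predose assessment may be repeated if the results are considered unreliable or of unacceptable quality by the Investigator". The rule that follows is: "In the case of repeat assessments, the measure reflecting the average of the measures will be considered the Baseline value". The SAP introduction takes precedence: "The statistical analysis methods presented in this document will supersede the statistical analysis methods described in the clinical protocol". For exams planned once, SAP 7.3 reads: "NIRAF, SD-OCT, and ERG, planned to be done once at baseline, the average will be defined as baseline if the exam is repeated". SAP 14.3 to 14.5 add "Baseline PLR is the average of all pre-dose PLR assessments", "Baseline OCI is the average of all pre-dose OCI assessments" and "Baseline ERG is the average of all pre-dose ERG assessments for that light/dark adaptive condition". SAP 14.6 (SD-OCT) and 14.7 (NIRAF) average repeated pre-dose exams and use every measure whatever its confidence score. FST is not part of this second point, because SAP 14.2 already provides an analysis of successful thresholds only.

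**The concern.** An eye chosen because one noisy reading was poor has, on average, a reading that was too poor. The other eye's reading was, on average, too good. If the same reading then enters the baseline, later readings drift back toward the truth. The treated eye appears to gain and the contralateral eye appears to lose, even if the drug does nothing. Masked reading does not prevent this, because the error comes from selection, and BCVA is not among the assessments that SAP 4.1 lists as masked.

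The trial is open-label with no randomised control, so these two contrasts carry the efficacy reading. That reading has uses: Protocol 7.5 bases the extension decision partly on efficacy, and 4.2.4 allows a recommendation to stop for overwhelming efficacy.

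The second issue is different in kind. A reading judged unfit and replaced by a repeat still counts toward baseline, which adds noise or a shift of either sign.

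**Working it through.** The documents give no test-retest SD, no between-eye gap and no power calculation, so there is no stated figure to reproduce. The size has to be shown over assumed ranges.

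**1. Selection bias in BCVA**

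Inputs from the documents: selection on the Screening reading; baseline = mean of Screening and Day 1, so each planned reading has weight 1/2.

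Assumptions: normal errors with single-reading SD s; true between-eye gap d; inter-eye error correlation rho within a visit; errors independent between visits; no drug effect.

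Let tau = s × sqrt(2(1 − rho)), the SD of the between-eye error at one visit. Choosing the worse eye gives the Screening between-eye difference an expected error of 2 × tau × phi(d/tau), where phi is the standard normal density. Averaging with Day 1 halves it:

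between-eye bias in change = −tau × phi(d/tau); treated eye alone = half of that.

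For rho = 0 and d = 0: tau = 1.414s and phi(0) = 0.399, so the bias is −0.56s between eyes and −0.28s for the treated eye.

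| True gap d | Between eyes, rho = 0 | Treated eye, rho = 0 | Between eyes, rho = 0.5 |
|---|---|---|---|
| 0 | −0.56s | −0.28s | −0.40s |
| 1s | −0.44s | −0.22s | −0.24s |
| 2s | −0.21s | −0.10s | −0.05s |
| 3s | −0.06s | −0.03s | 0.00s |

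Negative logMAR change is apparent benefit. Simulation with 2,000,000 replicates per cell agreed within 0.003s, and a Day 1 baseline was within 0.002s of zero.

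If the gap instead varies between subjects around zero with SD g (rho = 0), the between-eye bias is −s² × sqrt(2/pi)/sqrt(g² + 2s²): −0.46s, −0.33s and −0.19s for g = s, 2s and 4s.

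In logMAR, for equal eyes with independent errors (0.564 × s): s = 0.05, 0.10, 0.20, 0.30 gives −0.028, −0.056, −0.113, −0.169.

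**2. Price of a Day 1 baseline**

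The between-eye change has variance 2 tau² with Day 1 as baseline. With the average it is about 1.5 tau² when d is large, and tau² × (1 + (2 − 2/pi)/4) = 1.34 tau² at d = 0. The SD ratios are sqrt(2/1.5) = 1.15 and sqrt(2/1.34) = 1.22.

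If Screening and Day 1 errors have correlation r that the post-dose reading does not share, the average's bias is multiplied by (1 + r), and Day 1 has 2r times the tabled bias. At d = 0 and rho = 0, r = 0.2 gives −0.23s for Day 1 against −0.68s for the average; r = 0.4 gives −0.45s against −0.79s.

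**3. Weight of a rejected reading**

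After one repeat, a rejected reading with error b shifts baseline by b/2 for ERG, SD-OCT or NIRAF (two readings) and by b/3 for PLR or OCI (Screening, Day 1 and the repeat).

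If its error SD is k × s and there is no systematic shift, leaving it out lowers the baseline SD only when sqrt(1 + k²)/2 > 1, so k > 1.73, or when sqrt(2 + k²)/3 > 1/sqrt(2), so k > 1.58.

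**The case against.** **What stands.** The visible SAP tabulates each eye separately and specifies no treated-minus-contralateral statistic, so its tables carry the per-eye figure, half of the between-eye one. The bias is small when the eyes clearly differ. The weight of 1/2 holds only for the two planned readings. Where acuities tie, Screening acuity does not choose the eye. A Day 1 baseline is noisier: on mean squared error with independent eyes it beats the average at n = 11 (SAP 7.6) only if d is below about 1.5s, and never in a cohort of 2. Two interim analyses have been run, so a new summary cannot be called prespecified. The separate inferential SAP and the Imaging Charter are not shown and may deal with either issue.

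**Stronger readings that a reader might infer.**
- *That the 0.3 logMAR flag in the BCVA listing favours the treated eye.* Change is follow-up minus baseline, and higher logMAR is worse. A change of at least 0.3 therefore marks worsening if read literally, or a change in either direction. An either-direction flag hits both eyes equally under this model, by symmetry (22% and 22% at an assumed s of 0.2). A literal one would flag the treated eye less often.
- *That the 1.0 logMAR steps between light perception, hand movement and counting fingers make the bias much larger.* Those values are used only when neither chart nor Berkeley test gives a logMAR value. A light-perception eye cannot read a step worse and stay eligible. With one-sided moves of assumed probability 0.05, 0.10 or 0.20, its between-eye bias is about −0.05, −0.09 or −0.16 logMAR, half of what two-sided moves would give.
- *That rejected readings should simply be excluded.* That would let an unmasked judgement set the baseline, against an explicit all-measures rule for SD-OCT and NIRAF. By step 3 it helps only if the rejected reading was considerably noisier than usual or shifted.

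**Conclusion.** The main point holds. Reusing the selecting Screening reading in the BCVA baseline biases the treated-eye change toward benefit in expectation, with the between-eye contrast affected twice as much. The direction follows from the stated rules. The size rests on assumed normal errors and on s, d and rho, none of which the documents supply; the tabled values are illustrations and not bounds.

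The secondary point holds on the visible text only: a reading repeated for poor quality keeps a weight of 1/2 or 1/3 after one repeat, with no fixed direction of error.

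Severity is minor. Safety is the primary endpoint, Protocol 4.1.3 says the study is not powered for efficacy, and the visible SAP is descriptive.

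**What to change.** 1. **SAP 14.1.** Keep the two-visit average as the planned BCVA baseline. Add one supplementary change summary with the Day 1 pre-dose reading as baseline, for treated and contralateral eyes, all treated subjects combined and not by cohort. Label it as added after the interim analyses. Do the same for FST or mobility course in subjects where that measure broke an acuity tie.

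   Cost: one table from readings the plan already schedules. The SD of the between-eye change is 15% to 22% larger, and Day 1 keeps some bias if Screening and Day 1 errors are correlated. It therefore stands beside the average and does not replace it.

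2. **SAP 7.3 and 14.3 to 14.7.** Keep the planned averages. Where source records show that a reading was rejected for quality and repeated, list it and give the change from baseline with and without it as a sensitivity analysis. Treat repeated post-dose exams the same way. If the Imaging Charter already has a rule, cite it.

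   Cost: one listing and a short re-run. Protocol 8.12 requires attempts to be recorded but not a rejection status, so this covers only the cases that source records can identify.

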## **9.0 ASSESSMENT OF SAFETY OR ADVERSE EVENTS AND SERIOUS ADVERSE EVENTS**

All subjects who receive study drug will be assessed for safety.

Investigators are responsible for monitoring the safety of subjects who have entered this study and for alerting the Sponsor regarding any event that seems unusual, even if this event may be considered an unanticipated benefit to the subject. The Investigator is responsible for appropriate medical care of subjects during the study.

### **9.1 Data Monitoring Committee**

An independent DMC will provide safety oversight for the study. A DMC operational charter will be finalized and an initial organizational meeting held prior to screening of the first subject.

Once the first 2 adult subjects have been dosed and safety and tolerability data for at least 4 weeks post dose are available, the DMC will review safety and tolerability data, and provide their recommendation for proceeding to the next dosing cohort, as described in [Section 4.2.2](#) and the DMC Charter.

## **9.2 Definitions of Adverse Event, Serious Adverse Event, and Suspected Unexpected Serious Adverse Event**

### **9.2.1 Adverse Events**

An AE is any untoward medical occurrence associated with the use of a drug in humans, whether considered drug related or not. Adverse events can include any unfavorable, noxious, unintended sign, symptom, or disease temporally associated with use of a study drug or other protocol-imposed intervention, regardless of attribution. Adverse events may be spontaneously reported by the subject, discovered by Investigator questioning, or detected through physical examination, laboratory test, or other means.

Adverse events include:

- Pre-existing medical conditions judged by the Investigator to have worsened in severity or frequency or changed in character during the protocol-specified AE reporting period (as specified in [Section 9.4.1](#))
- Adverse events not previously observed in the subject that emerge during the protocol-specified AE reporting period (as specified in [Section 9.4.1](#))
- Complications that occur as a result of protocol-mandated interventions (eg, invasive procedures such as IVT injections)
- Adverse events that occur prior to study treatment that are related to a protocol-mandated intervention (eg, invasive procedures such as blood draws, anesthesia prior to IVT injection)

### **9.2.2 Serious Adverse Events**

An SAE is any AE that suggests a significant hazard, contraindication, side effect, or precaution regardless of the relationship to study drug. An SAE is any AE that results in any of the following outcomes:

- Death
- Life-threatening AE. This definition implies that the subject, in the view of the Investigator, is at immediate risk of death from the event as it occurred. It does not include an event that, had it occurred in a more severe form, might have caused death
- Inpatient hospitalization or prolongs existing hospitalization, except for hospitalization for planned post dose sample collections

- Persistent or significant disability/incapacity (ie, the AE results in substantial disruption of the subject's ability to conduct normal life functions)
- Congenital anomaly or birth defect. This serious criterion applies if a congenital anomaly/birth defect is diagnosed in a child born to a female subject, or a female partner of a male subject exposed to the study drug
- Other important medical events. Medical and scientific judgment should determine whether an AE should be classified as serious in other situations, such as important medical events that may not be immediately life-threatening or result in death or hospitalization, but may jeopardize the subject or require intervention to prevent one of the outcomes listed in the definition above.

All AEs that do not meet any of the criteria for serious should be regarded as non-serious AEs.

The terms “severe” and “serious” are not synonymous. Severity refers to the intensity of an AE (as in mild, moderate, or severe pain); the event itself may be of relatively minor medical significance (such as severe headache) (See [Section 9.3.1](#)). “Serious” is a regulatory definition and is based on subject or event outcome or action criteria usually associated with events that pose a threat to a subject’s life or vital functions. Seriousness (not severity) serves as the guide for defining regulatory reporting obligations.

Severity and seriousness should be independently assessed when recording AEs and SAEs on the AE eCRF and SAE form.

